7.2.3 Causality Assessments

The investigator will use medical consideration to determine the potential relationship of the AE to the study drugs based on his/her clinical judgment. Assessment of causality will be based upon the following:

- Alternative possible causes of the AE, including the subject's underlying disease or co-morbid conditions, other drugs, other host and environmental factors;
- The temporal sequence between the exposure to study drug and the AE;
- Whether the clinical or laboratory manifestations of the AE are consistent with known actions or previously reported toxicity of the study drug (or similar drugs);
- Whether the AE resolved or improved with decreasing the dose or stopping the study drug (ie, dechallenge); or recurred or worsened with re-exposure to the drug (ie, rechallenge).

The relationship between the study drug and the AE will be described using one of the following categories:

- Unrelated: Another factor is clearly the cause of the AE.
- Possibly Related: There is a reasonable possibility that the study drug is the cause of the AE, including that the study drug and another factor(s) are equally likely as causes of the AE.
- Related: The AE can be fully explained by the administration of study drug.

7.3 Documenting Adverse Events (AEs)

All AEs (including SAEs) are to be accurately recorded on the Adverse Event page of the subject's electronic CRF from the time the subject signs the informed consent until the Post-Treatment Safety visit. Each event will be assessed for serious criteria, severity, and causality (see "Causality Assessments"). The date of onset, as well as the duration of the event will be recorded. In addition, treatments provided to the subject, actions taken with the study drugs, and the outcome of the AE will also be noted.

7.4 Reporting Serious Adverse Events (SAEs)

Time Frame for Reporting

SAEs must be reported to the Sponsor or Sponsor's designee (within 24 hours) of becoming aware of the event (regardless of the initiation of any new anticancer therapy) including the following:

- Any death or SAE experienced by the subject from the signing of informed consent to 30 days after the last dose of study drug, regardless of relationship to study drug.
- Any death or SAE that the Investigator becomes aware of, and believes to be study drug related, that occurs more than 30 days after the subject last received study drug.

Study drug-related AEs/SAEs that are ongoing at the time of the Post-Treatment Safety Assessment visit should continue to be followed until resolution, return to baseline, or until they have stabilized or become chronic (and following consultation and agreement by the ZIOPHARM Medical Monitor).

Information to be provided by the Investigator

Within 24 hours of becoming aware of the SAE or subject death, the investigator must notify the Sponsor or designee and transmit information to the Sponsor or designee. Information (initial and follow-up) should be provided on an electronic and/or paper SAE Report form signed and dated by the investigator. The SAE Report form and copies of source documents (with subject identifiers redacted) will be transmitted by fax. A hospital discharge summary should be provided if the subject was hospitalized. An SAE report will be considered final once all relevant information has been received and reviewed by the Sponsor.

The SAE Report form is provided in the investigator study files. Please refer to the investigator study files for instructions on how to complete the form. The investigator will provide all of the following information related to the event:

- Investigator identification
- Subject identification (e.g., subject number, initials, sex, age or date of birth)
- Information regarding study drug administration (e.g., start/stop date, dose, and frequency)
- Description of event
- Action taken with the study drugs in relation to the SAE
- Outcome of the SAE

In addition to the above information, the investigator must provide, for each event term, an assessment of:

- Severity/intensity
- Relationship to the study drug (causality assessment)

7.5 Sponsor and Investigator Responsibility for Reporting Adverse Events (AEs)

All AEs and SAEs will be reported to regulatory authorities, IRBs/IECs, and investigators in accordance with all applicable global laws and regulations. The investigator must submit all Safety Letters from the Sponsor to his/her IRB/IEC per agreements and local requirements. The investigator must keep copies of all safety reports, including correspondence with ZIOPHARM and the IRB/IEC, in the study file.

7.6 Follow-up Information

Appropriate diagnostic tests should be performed and therapeutic measures, as medically indicated, should be instituted. Appropriate consultation and follow-up evaluations should be carried out until the event has resolved, stabilized, returned to baseline, or is otherwise explained by the investigator.

Follow-up data concerning the SAE (eg, diagnostic test reports, hospital summaries, etc.) must be promptly reported (within 24 hours of receipt) to the Sponsor or Sponsor's designee, until resolution of the SAE. Should the FDA or National Regulatory Authorities require that the Sponsor submit additional data on the event, the investigator will be asked to provide those data to the Sponsor in a timely fashion.

Required Follow-up for Serious Adverse Events (SAEs)

All treatment-related AEs/SAEs that are ongoing at the time of the Post-Treatment Safety visit will be followed until:

- The event resolves, or
- The event returns to baseline if a baseline value is available, or
- The event stabilizes (and following consultation and agreement by the ZIOPHARM Medical Monitor), or
- The event can be attributed to factors other than the study drug or other than study procedure.

7.7 Pregnancies

Subjects who become pregnant during the study should immediately discontinue participation in the study. The Sponsor should be immediately notified.

An initial Pregnancy Report form and a Pregnancy Outcome Form are to be completed by the investigator or designee. The Pregnancy Report form and the completion guidelines will be provided in the investigator study files. Please refer to the investigator study files for details on how to complete these forms.

8. STATISTICAL PROCEDURES

Data from this study will be analyzed and included in a clinical study report that will be prepared after the last subject has completed the Post-Treatment Safety Assessment visit. Additional data collected from subjects who have not progressed by the Follow-Up Tumor Assessment visit and are continuing to be followed for tumor response at the time of the final data cut-off date will be presented in an addendum to the study report.

8.1 Determination of Sample Size

In view of up to 3 novel investigational drugs being tested in this study, the sponsor has incorporated a Safety Run-in (Part 1) to evaluate safety for each study arm before fully enrolling all subjects required in Stage 1 of Part 2 for each study arm (for details please see [Section 5.1.1](#)).

The sample size of Part 2 is determined based on a Simon 2-stage design for each study arm. For Ad-RTS-hIL-12 monotherapy (Arm A) with 13 subjects evaluated in Stage 1 and an additional 20 subjects in Stage 2 if applicable, it will provide 80% power at 1-sided 5% significance level to differentiate 35% targeted proportion of subjects who survive progression-free at week 16 from a proportion of no interest of 15%. If ≥ 3 of 13 subjects survived progression-free at week 16 in Stage 1, 20 additional subjects will be evaluated in Stage 2.

For the Ad-RTS-hIL-12 + palifosfamide combination (Arm C), with 12 subjects evaluated in Stage 1 and an additional 14 subjects evaluated in Stage 2, it will provide 80% power at 1-sided 5% significance level to differentiate 65% targeted proportion of subjects who survive progression-free at week 16 from a proportion of no interest of 40%. If ≥ 6 of 12 subjects survived progression-free at week 16 in Stage 1, 14 additional subjects will be evaluated in Stage 2.

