2. PROTOCOL SYNOPSIS

Title	A Phase II, Randomized, Open-Label Study of Ad-RTS-hIL-12 Monotherapy or Combination with Palifosfamide in Subjects with Recurrent/Metastatic Breast Cancer and Accessible Lesions
Protocol Number	ATI001-201
Study Sponsor	ZIOPHARM Oncology, Inc.
Clinical Phase	II
Objectives	
Primary Objectives:
 
• Assess the safety and tolerability of INXN-1001 (activator ligand) + INXN-2001 (Ad-RTS-hIL-12) as monotherapy and in combination with palifosfamide in subjects with recurrent and/or metastatic adenocarcinoma of the breast with accessible lesions• Assess the efficacy of repeated cycles of intratumoral (IT) injections of INXN-2001 (Ad-RTS-hIL-12) with INXN-1001 (oral activator ligand) as monotherapy or in combination with palifosfamide as measured by the 16-week progression-free survival (PFS) rate 
Secondary Objectives:
 
• Estimate PFS by modified Response Evaluation Criteria in Solid Tumors (mRECIST) v1.1• Assess objective response rate (ORR) by mRECIST v1.1• Assess duration of response• Assess clinical benefit rate• Evaluate pharmacodynamic tumor markers (eg, breast cancer-associated biomarkers such as MUC-1)• Assess the pharmacokinetics (PK) of INXN-1001
Study Drugs	INXN-1001 (oral activator ligand) INXN-2001 (Ad-RTS-hIL-12) Palifosfamide
No. Centers	Multicenter (approximately 30 centers in the US)
Anticipated No. of Subjects	Approximately 9 subjects, up to 62 subjects 
• Part 1 Safety Run-in: approximately 9 subjects• Part 2 Randomization: up to 53 subjects
Study Design	This is a multicenter, open-label, randomized, Phase II study to evaluate the safety and efficacy of INXN-1001 + INXN-2001 (to be

[figure not shown]
referred to as “Ad-RTS-hIL-12 monotherapy” or Arm A) and INXN-1001 + INXN-2001 with palifosfamide (to be referred to as “Combination therapy” or Arm C) in subjects with recurrent/metastatic breast cancer with accessible tumor(s). (Table 1 and Figure 1)

Part 1 is a safety run-in where a safety assessment will be made after 1 cycle of therapy.

In **Part 2**, eligible subjects will be randomly assigned to active treatment Arms A or C. Various futility analyses based on PFS at week 16 have been incorporated in both arms as described below.

Table 1: Study Design

Part	Treatment Arm	Intervention (21-day cycle)

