1 Safety Run-in	A	Ad-RTS-hIL-12 monotherapy; n=6 [INXN-1001 (140 mg daily) + INXN-2001 (███████████)]
	C	Combination therapy; n=3 [INXN-1001 (140 mg daily) + INXN-2001 ██████████ ██████████ + palifosfamide (120 mg/m ²)]
2 Randomization	A	Ad-RTS-hIL-12 monotherapy [INXN-1001 (140 mg daily) + INXN-2001 ██████████ 10 ¹² vp)]
	C	Combination therapy [INXN-1001 (140 mg daily) + INXN-2001 ██████████ ██████████ + palifosfamide (120 mg/m ²)]

	
treatment, then this treatment arm will be included in Part 2 of the study.
 
During Part 2, 9 additional subjects will be randomly assigned to Arm C. If <6 of the first 12 (3+9) subjects survive progression-free at week 16, no additional subjects will be enrolled. If ≥ 6 of the 12 subjects survive progression-free at week 16, an additional 14 subjects will be randomly assigned. If ≥ 15 of the 26 (3 + 9 + 14) subjects in the expansion cohort survive progression-free at week 16, then this regimen would be considered worthy of further investigation (ie, a confirmatory trial).
 
The primary efficacy endpoint is the 16-week PFS rate, defined as the proportion of subjects that remain progression-free at week 16 by mRECIST v1.1 for Arms A and C. Futility decisions will be made using results at week 16 from both primary and secondary endpoints.
 
The safety of study treatments will be assessed throughout the study by the frequency and severity of adverse events (AEs) as determined by the National Cancer Institute (NCI) Common Terminology Criteria for Adverse Events (CTCAE) v4.03.
 
An SRC meeting can be convened if deemed necessary by the sponsor or the investigators at any point during the study.

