3.5 Rationale for Study Design and Dose Selection

The objectives of this Phase II clinical trial are to assess the safety and tolerability, PFS rate at 16 weeks, ORR, and immunological and biological effects of IT injections of INXN-2001 + INXN-1001 as monotherapy or in combination with palifosfamide. To provide an opportunity to monitor the safety of Ad-RTS-hIL-12 monotherapy and Ad-RTS-hIL-12 + palifosfamide (combination therapy) in subjects with breast cancer, a safety run-in will occur, with evaluation following one cycle of study drug.

The study will commence with Ad-RTS-hIL-12 monotherapy using a 140-mg dose of INXN-1001 administered daily Days 1-7 in 6 subjects (21-day cycle). Following a safety assessment, combination therapy of Ad-RTS-hIL-12 + palifosfamide (120 mg/m², Days 1, 2, 3 of a 21-day cycle, n=3) will commence. Safety in Part 1 of the study will determine commencement of randomization for Part 2.

During the conduct of this study, in addition to monitoring of safety and therapeutic efficacy, peripheral blood samples will be studied for indications of immunological and biological effects including analyses of breast cancer-associated cytokines/biomarkers. The combined clinical and laboratory data will be studied to assess for activity, and will be used in decision making for expansion of treatment arms.

The population for this study was selected as those subjects with recurrent or metastatic breast cancer (which is rarely curable with standard therapy) and accessible lesions, who are therefore considered to be appropriate candidates for clinical trials exploring new forms of treatment. Because breast cancers may be responsive to immunotherapeutic approaches (see [Section 4.1 Disease Background](#)), this subject population may potentially benefit from investigational therapy with Ad-RTS-hIL-12 alone or in combination with palifosfamide.

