4.1.5 Treatment Arm Expansion Procedure

Should a subject discontinue study treatment before receiving 6 cycles for reasons other than progression, another subject may be added to the treatment arm to allow for full analysis. Response evaluation and criteria for futility are described in [Section 9 Statistical Methods](#).

Subject enrollment and expansion of treatment Arms A and C will proceed according to a standard Simon 2-stage design ([Table 1](#)). An alternate dose level of palifosfamide and/or INXN-1001 may be explored after review of all available safety and activity data, and will be communicated by an administrative letter and enacted upon issuance.

Table 1 Study Design (see Protocol Synopsis)

Part	Treatment Arm	Intervention (21-day cycle)
1 Safety Run-in	A	Ad-RTS-hIL-12 monotherapy (n=6) [INXN-1001 (140 mg daily) + INXN-2001 [REDACTED] [REDACTED] [REDACTED]
	C	Combination therapy; n=3 [INXN-1001 (140 mg daily) + INXN-2001 [REDACTED] [REDACTED] [REDACTED] + palifosfamide (120 mg/m ²)]
2 Randomization	A	Ad-RTS-hIL-12 monotherapy [INXN-1001 (140 mg daily) + INXN-2001 [REDACTED] [REDACTED] [REDACTED]
	C	Combination therapy [INXN-1001 (140 mg daily) + INXN-2001 [REDACTED] [REDACTED] [REDACTED] + palifosfamide (120 mg/m ²)]

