5.4 Replacement of Subjects

Should a subject discontinue study treatment before receiving 6 cycles for reasons other than progression, another subject may be added to that study arm for full analysis.

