Global change: Pharmacokinetic assessment added Part 1 Arm A	PK assessments were added at the following time points for Arm A Cycles 1 and 2: Blood samples for PK analysis of INXN-1001 for Part 1 treatment Arm A CYCLE 1 ONLY should be obtained on the following days and time points: Day 1: [6 samples] Pre-dose (\leq30 minutes prior to INXN-1001 dosing), 0.5, 1, 2, 4, 6 hours post-INXN-1001 dosing Day 2: [1 sample] Pre-dose (\leq 30 minutes prior to INXN-1001 dosing) Day 7: [3 samples] Pre-dose (\leq 30 minutes prior to INXN-1001 dosing), 1-2 hours, 4-6 hours post-INXN-1001 dosing Day 8: [1 sample] 24 ± 3 hours post-Day 7 INXN-1001 dose	PK assessment will facilitate and understanding of drug levels and the safety profile for the treatment with study drug
Global change: Study Design Arm A Ad-RTS-hIL-12 Monotherapy has 2 cohorts	Added text: A dose escalation of INXN-1001 will be evaluated with 3 subjects in each cohort of Arm A with safety assessment: During Part 1, Arm A will explore the safety of Ad-RTS-hIL-12 monotherapy in 2 cohorts, 3 subjects each. Arm A will enroll cohort 1 at 140 mg INXN-1001 (n=3), and cohort 2 at 160 mg INXN-1001 (n=3). If Ad-RTS-hIL-12 monotherapy is tolerable in 6 subjects (cohorts 1 and 2), then 3 additional subjects will be enrolled during Part 2 for efficacy analysis. All additional subjects enrolled in Part 2 will be at the 160-mg dose of INXN-1001. Futility decisions will be made based on activity observed in subjects receiving INXN-1001 at the 160-mg dose only. If at least one of the 6 subjects (3 + 3) survives progression-free at week 16, then Arm A will be expanded with 7 additional subjects to be randomly assigned to Arm A. These first 13 subjects (6 + 7) on Arm A will undergo tumor assessment for progressive disease (PD) after 16 weeks of treatment. If ≥ 3 of these 13 subjects survive progression-free at week 16, this stage will be expanded to include 20 additional randomly assigned subjects. If ≥ 9 of these 33 (13 + 20) subjects survive progression-free at week 16, then this regimen would be considered worthy of further investigation (ie, a confirmatory trial).	A stepped approach with INXN-1001 dosing will allow for a run-in safety analysis for the study treatment

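### Arm A's stated 80% power belongs to the plain two-stage rule; applying the synopsis's 1-of-6 condition as binding gives 78.0%.

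*Protocol*

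**What the plan says.** Section 8.1 bases Part 2 on a Simon two-stage design for each arm. For Arm A, 13 subjects are evaluated in Stage 1 and 20 more in Stage 2. The section states that "it will provide 80% power at 1-sided 5% significance level to differentiate 35% targeted proportion" "from a proportion of no interest of 15" percent. The only continuation rule it gives for this arm is at least 3 of 13. Section 4.1.5 likewise calls the expansion a standard two-stage design.

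The Sample Size text of the synopsis lists three successive week-16 conditions for Arm A:

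- at least 1 of the first 6 progression-free, after which 7 are added to complete the 13 of Stage 1;
- at least 3 of 13, after which 20 are added;
- at least 9 of 33, after which a confirmatory trial is considered.

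The first condition has the same if-then form as the second and uses the same endpoint. Arm C has no corresponding early condition. The supplied SAP does not settle the matter: its sections 5.2 and 5.4 describe a single-arm study of at most 40 subjects and contain no such rule.

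**The concern.** The synopsis and section 8.1 describe different rules for the same 13 subjects, and only one of them can carry the stated power. An added futility look can only remove paths to success, so it lowers both power and type I error. If the 80% was worked out without the look, Arm A has less power than stated whenever the look is enforced. A reader of section 8.1 alone would also not know that the arm could close after 6 subjects.

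**Working it through.** **Inputs.** Rate of no interest 0.15, target rate 0.35, 13 + 20 subjects and continuation at 3 of 13 or more come from section 8.1 and the synopsis. The final count of 9 of 33 and the look at 6 (6 + 7 = 13) come from the synopsis Sample Size text.

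**1. Reproduce the stated figure (no look at 6).**

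P(success) = Σ over x = 3..13 of P(Bin(13, p) = x) × P(Bin(20, p) ≥ 9 − x)

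At p = 0.35:

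| x of 13 | P(x) | P(enough in the next 20) | Product |
|---|---|---|---|
| 3 | 0.1651 | 0.7546 | 0.1246 |
| 4 | 0.2222 | 0.8818 | 0.1960 |
| 5 | 0.2154 | 0.9556 | 0.2058 |
| 6 | 0.1546 | 0.9879 | 0.1528 |
| 7 | 0.0833 | 0.9979 | 0.0831 |
| 8 or more | | | 0.0462 |

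The unrounded total is **0.8084**. The same sum at p = 0.15 gives **0.0412**. The stated 80% at one-sided 5% is therefore reproduced by the plain two-stage rule.

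**2. Apply the 1-of-6 condition as binding.** The paths removed are those with 0 of the first 6, at least 3 of the next 7, and a final total of at least 9:

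Loss = (1 − p)^6 × Σ over c = 3..7 of P(Bin(7, p) = c) × P(Bin(20, p) ≥ 9 − c)

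At p = 0.35, 0.65^6 = 0.0754, and the terms are:

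- c = 3: 0.0754 × 0.2679 × 0.7546 = 0.0152
- c = 4: 0.0754 × 0.1442 × 0.8818 = 0.0096
- c = 5: 0.0754 × 0.0466 × 0.9556 = 0.0034
- c = 6 and 7: 0.0006 together

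The unrounded loss is 0.0289, so power = 0.8084 − 0.0289 = **0.7795**. At p = 0.15 the loss is 0.0024, so type I error = 0.0412 − 0.0024 = **0.0388**.

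**3. How much stopping is new?** A subject series with 0 of 6 and then at most 2 of 7 fails the 3-of-13 rule anyway.

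| True rate | P(0 of 6) | Would also stop at 3 of 13 | Extra stopping |
|---|---|---|---|
| 0.35 | 0.0754 | 0.0754 × 0.5323 = 0.0401 | 0.0353 |
| 0.15 | 0.3771 | 0.3771 × 0.9262 = 0.3493 | 0.0278 |

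**4. Cross-check on Arm C.** At least 6 of 12, then at least 15 of 26, gives power 0.8086 at 0.65 and type I error 0.0469 at 0.40. This agrees with section 8.1, so the mismatch is confined to Arm A.

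**The case against.** **Section 8.1 contains no arithmetic error.** It attributes 80% to a two-stage design, and that design gives 80.8%. This stands: the defect is a mismatch between the synopsis and the body text, not a miscalculation.

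**The look may not bind.** The Arm A part of the synopsis Study Design narrative is absent from the text available. For Arm C the narrative spells out that enrolment ends if the count is missed; for Arm A only the short conditional wording remains. The synopsis also says that "Futility decisions will be made using results at week 16 from both primary and secondary endpoints", so the count might be overruled. This stands too, and is why the result is given as a range. It does not remove the mismatch, since nothing available calls the look advisory.

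**The effect is slight.** Without the look, a true rate of 34% instead of 35% already lowers power to 77.8%. That is fair, and it limits the weight of the point without making the stated figure match the rule.

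**Stronger readings that the documents do not support.**

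- A reader might infer that the whole 7.5% chance of 0 of 6 at the target rate is unaccounted for. It is not: 4.0 of those points would stop at 3 of 13 and are already reflected in the 80.8%.
- A reader might infer that false-positive control is threatened. An added futility look lowers type I error.
- A reader might infer a wrong sample size, because the stage sizes sum to 33 + 26 = 59, or 50 in Part 2, against ceilings of 62 and "Part 2 Randomization: up to 53 subjects". Those are maxima, and section 5.4 provides that "another subject may be added to that study arm for full analysis", so they show no sizing error.
- How secondary endpoints enter futility decisions is a separate question. Here it bears only on whether the look binds.

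**Conclusion.** The point holds as an inconsistency of modest size. The 80% in section 8.1 is the power of a rule without the 1-of-6 condition. With that condition binding, and the first 6 counted among the 13, Arm A has 78.0% power, about 2 points below the stated figure and 2.9 below the plain rule. If the condition can be overruled, power lies between 78.0% and 80.8%, depending on how often that happens. Type I error is between 3.9% and 4.1%, below 5% in either case.

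The calculations are exact given the stated rates, independent subjects and all 33 counted. Whether the look binds is the one assumption that the available text cannot settle. No threshold or sample size needs to change.

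**What to change.** Choose one of two statements and make section 8.1 and the synopsis agree.

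- **Binding look.** Describe the 1-of-6 condition in section 8.1 and restate Arm A as about 78% power with type I error 3.9%. The cost is a stated power about 2 points lower.
- **Non-binding look.** Say in both section 8.1 and the synopsis that the look is advisory, and keep 80.8% and 4.1%. It would help to add that power falls to 78.0% if the look is always followed. The cost is some early-stopping benefit. If enrolment pauses at each look, which the available text does not state, expected Arm A size at the 15% rate is 6(0.3771) + 13(0.6229) + 20(0.2802) = 16.0 with the look enforced, against 13 + 20(0.3080) = 19.2 if it is never acted on.

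Either way the change is confined to text.
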